### **Region Analysis**

This exploratory analysis will be conducted to evaluate the impact of region on the primary treatment comparison. Each center will be classified as either US-based or Non-US based. In this analysis, the primary endpoint of normalized Hb AUC will be analyzed similarly to the primary analysis; however, region and the region\*treatment interaction will be included in the model as fixed effect terms. If the region\*treatment interaction term is significant at 0.05 significant level in the model, then the point estimates and associated 95% confidence intervals for the treatment differences may be calculated for each region.

### **RBC Storage Solution Analysis**

This exploratory analysis will be conducted to evaluate the impact of RBC storage solution on the primary treatment comparison. In this analysis, the primary endpoint of normalized Hb AUC will be analyzed similarly to the primary analysis; however, storage solution type will be included in the model as a fixed effect. If the storage solution type term is significant in the model, then the point estimates and associated 95% confidence intervals for the treatment differences may be calculated by storage solution type.

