10.2 Red Blood Cell Products

The RBCs to be utilized in this study will be as follows and will meet standard release criteria for transfusion:

- MIR RBCs: RBCs will be derived from WB collected in CPD solution, treated with the Mirasol System for WB, LR, and stored in AS-3 for \leq 21 days at 1 - 6°C.
- REF RBCs: LR apheresis RBCs or WB-derived RBCs will be per site standard inventory.

No other pathogen reduction treated blood products including platelets and/or plasma may be used for transfusion in subjects during study participation.

MIR RBCs will be prepared from WB treated with the Mirasol System for WB according to the Blood Processing and Storage Guidelines and the Mirasol System for WB Illuminator Operator's Manual.

The MIR RBCs must not be irradiated. Irradiating blood products that have been Mirasol-treated is redundant and may further compromise RBC viability. In vitro studies demonstrated Mirasol treatment was as effective as irradiation in preventing leukocyte proliferation and was more effective than gamma irradiation at preventing antigen presentation, cytokine production, and T-cell activation.

Modifications such as RBC washing (MIR RBCs or REF RBCs) or irradiation (REF RBCs only) may be done according to Hospital Site and/or Local Blood Center standard procedures and following established guidelines as to impact to storage durations and transfusion practices. Any modifications will be captured in the electronic case report form (eCRF). Anticipated incidence of washing is 35% for conventional RBCs and 33% for irradiated RBCs.³⁰

Mirasol increases extracellular potassium in WB derived RBC products. Use with caution in patients at risk of hyperkalemia (eg, patients with renal failure) and/or requiring administration via central venous access device.

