13.2 Reference RBCs

The Local Blood Bank at each Hospital Site will be responsible for acquiring REF RBC product from their routine use inventory.

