13.3 Data Collection and Procedures for RBC Units

Data will be recorded in source documents and entered into eCRFs for each MIR RBC, REF RBC, and off-protocol unit unless otherwise noted. Table 13-1 summarizes these procedures.

1. RBC product details:

- a. Blood Unit Identification (BUI) number
- b. Donation type (WB or apheresis, REF RBCs only)
- c. Donation collection date

- d. ABO and Rh type of unit
- e. Unit expiry date
- f. Washed RBCs (yes/no)
- g. Irradiated RBCs (yes/no; date) (REF RBC only)

2. Mirasol treatment details (MIR RBCs only)
 - a. Mirasol Illuminator serial number
 - b. Mirasol Whole Blood disposable set lot number
 - c. Donation collection start time
 - d. Mirasol Illumination start date/time
 - e. Date/time MIR RBCs placed in refrigerated storage
3. Product disposition (MIR RBCs only)

Table 13-1: Blood Center Procedures and Data Collection

	MIR RBCs	REF RBCs
Blood Unit Identification (BUI) number	X	X
Donation type (WB or apheresis) ^a		X
Donation collection date	X	X ^b
ABO and Rh type of unit	X	X
Unit Expiry date	X	X
Washed RBCs (yes/no)	X	X
Irradiated RBCs (yes/no; date)		X
Mirasol Illuminator serial number	X	
Mirasol Whole Blood disposable set lot number	X	
Donation collection start time	X	
Mirasol Illumination start date/time	X	
Date/time MIR RBCs placed in refrigerated storage	X	
Product disposition	X	

^a MIR RBCs derived from WB only. REF RBC may be derived from WB or via apheresis.

^b REF RBC: Record collection date if available.

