## **V. Interventions**

### **A. Clinical Trial Material**

The RBCs to be utilized in this study will be as follows and will meet standard release criteria for transfusion.

- MIR RBCs: RBCs will be derived from WB collected in citrate phosphate dextrose (CPD) solution, treated with the Mirasol System for WB, LR, and stored in Additive Solution Formula 3 (AS-3) for  $\leq$  21 days at 1 - 6°C.
- REF RBCs: LR apheresis RBCs or WB-derived RBCs will be per site standard inventory.

No other pathogen reduction treated blood products including platelets and/or plasma may be used for transfusion in subjects during study participation.

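### Every Mirasol unit is in AS-3, so the exploratory storage-solution analysis can give a same-solution treatment difference for AS-3 only, and its trigger does not test whether the treatment effect varies

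*SAP*

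**What the plan says.** **The products.** MIR units are fixed to one additive solution. Protocol 10.2 describes them as "treated with the Mirasol System for WB, LR, and stored in AS-3 for" at most 21 days, and SAP V.A agrees ("stored in Additive Solution Formula 3 (AS-3) for" the same period). The comparator has no fixed solution: "REF RBCs: LR apheresis RBCs or WB-derived RBCs will be per site standard inventory". Protocol 13.2 makes each hospital's local blood bank "responsible for acquiring REF RBC product from their routine use inventory".

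**The analysis.** SAP VIII.B, RBC Storage Solution Analysis, repeats the primary model with solution type added as a fixed effect. It plans no solution-by-treatment interaction and gives no significance level. The next step, which allows separate results for each solution, is conditional. Its rule begins: "If the storage solution type term is significant in the model, then the point estimates and associated 95% confidence intervals for the treatment differences". The analysis is labelled exploratory.

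**The data.** Protocol 13.3 opens with "Data will be recorded in source documents and entered into eCRFs for each MIR RBC, REF RBC, and off-protocol unit unless otherwise noted". The list and Table 13-1 then name the unit number, donation type, collection date, ABO/Rh, expiry, washing, irradiation and the Mirasol processing details. The nearest REF product descriptor is "Donation type (WB or apheresis, REF RBCs only"). Additive solution is not named. Protocol 14.3 asks for the type of product at each study transfusion and names the ISBT code for off-protocol RBCs.

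**The concern.** The analysis is meant to show whether the additive solution affects the MIR versus REF comparison. That calls for MIR and REF data in more than one solution, and MIR exists in only one. Reporting treatment differences by solution after a significant solution term would invite the reader to see effect modification that neither the test nor the data can show.

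The treatment estimate also changes meaning. In the primary model the comparator is REF as supplied. Once solution is in the model, the comparator is AS-3 REF, which may be a small part of the REF data. A reader could take the result for the primary comparison with a nuisance factor removed. Finally, the analysis needs the solution of each REF unit, and the protocol does not explicitly list that item.

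**Working it through.** The SAP gives no figure for this analysis, so the check is one of estimability.

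**Inputs.** MIR: AS-3 only (Protocol 10.2, SAP V.A). REF: unspecified (SAP V.A, Protocol 13.2). Assumption for illustration: four solutions in use, AS-3 and three others.

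**1. Which cells exist.** Two products by four solutions give 2 × 4 = 8 cells.
- REF in all four solutions: 1 MIR cell + 4 REF cells = 5 of 8.
- REF in the three other solutions only: 1 + 3 = 4 of 8.

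**2. Same-solution differences.** The difference at solution s is (MIR mean in s) − (REF mean in s). For any s other than AS-3 the MIR cell is empty. A rank check of the design agrees: with 5 cells, the difference is estimable at AS-3 and at none of the other three; with 4 cells, it is estimable nowhere. Running the model separately by solution does not help, since every non-AS-3 subset contains REF data only.

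**3. What the treatment term means.** For solution and treatment, write the mean of log AUC as a + t·MIR + b(s). This has 1 + 1 + 3 = 5 free parameters.
- With AS-3 REF present there are 5 cell means. Then t = MIR(AS-3) − REF(AS-3), and adding an interaction leaves the rank at 5.
- Without AS-3 REF there are 4 cell means for 5 parameters (rank 4). The MIR indicator and the AS-3 indicator are the same column, so t is fully aliased with solution.

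The contrast of MIR with REF in solution s is t + b(AS-3) − b(s). It can be computed in both cases, but outside AS-3 it includes the solution difference.

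**4. What the trigger tests.** Because MIR has one solution, a test of b(s) with treatment in the model compares REF solutions with each other. It does not ask whether t varies. The model inherits the treatment-by-period term, so t may differ by period, but it is the same for every solution by construction. The SAP's Region Analysis is built differently: it includes the region-by-treatment interaction, tests it at 0.05, and only then gives regional differences.

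**5. Precision of the AS-3 comparison.** Assume 77 subjects with 2 AUCs per product, so 77 × 2 = 154 AUCs each, treated as independent. If R of the 154 REF AUCs are in AS-3, the standard error relative to the full comparison is √[(1/154 + 1/R) / (2/154)].

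| Assumed AS-3 share of REF | R | SE ratio |
|---|---|---|
| 50% | 77 | 1.22 |
| 25% | 38 | 1.59 |
| 10% | 15 | 2.37 |
| 0% | 0 | not estimable |

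The within-subject correlation of a crossover would change these ratios; they show scale only.

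**6. Data availability.** Irradiation has its own analysis and its own field in Table 13-1. Additive solution has an analysis and no named field. The ISBT code is named for off-protocol RBCs, which SAP VIII.A keeps out of the primary analysis.

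**The case against.** The strongest defence is that the by-solution step can be read as MIR versus REF grouped by the REF unit's solution. Those contrasts can be estimated if the REF solution is known. If some REF units are in AS-3, the treatment term in the planned model is the like-for-like AS-3 comparison, and a solution-adjusted effect fits the stated aim. This stands. What remains is that the SAP does not say which contrast it means, that contrasts outside AS-3 mix treatment with solution, and that the trigger does not test effect modification.

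A reader might infer that the analysis can never separate Mirasol treatment from the additive solution. The documents do not support that. Complete aliasing arises only if no REF unit is in AS-3, and the mix of REF solutions is not given.

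A reader might also infer that the REF solution is not collected. That goes too far. The eCRF and the Manual of Procedures are not among the documents, the type of product is recorded for every study transfusion, and the unit number is recorded too. Naming the ISBT code for off-protocol units does not prove its absence for study units: volume and hematocrit appear in the same off-protocol list, and both are obtained for study transfusions elsewhere (Protocol 14.3.2 and 16.1.1). The supportable statement is that the solution is not explicitly listed.

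**Conclusion.** The point holds as a defect in one exploratory rule. A same-solution MIR-REF difference is available for AS-3 at most. The planned trigger and main-effect model cannot support treatment differences by solution, and the adjusted treatment term means MIR versus AS-3 REF.

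The AS-3-only restriction on MIR comes directly from the documents. The four solutions, the AS-3 shares and the independence of AUCs are assumptions. On them, the AS-3 comparison has a standard error about 1.2 to 2.4 times that of the full comparison for AS-3 shares from 50% down to 10%.

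The importance is low. Nothing here supports doubt about the primary result: the non-inferiority decision rests on the primary model and the limit of −0.2231, neither of which uses solution type.

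**What to change.** Replace the by-solution step in SAP VIII.B with:
- **(a)** MIR versus REF restricted to REF transfusion episodes given in AS-3, as the like-for-like comparison;
- **(b)** a comparison of solutions among REF episodes only.

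Label any contrast of MIR with non-AS-3 REF as mixing treatment with solution. State that the two cannot be separated if there is no AS-3 REF. Say how an episode with units in different solutions is classed; the SAP's analysis of units stored at most 21 days already has a rule of this kind. Confirm that the eCRF captures the additive solution of each REF unit, and add it to Table 13-1 if it does not.

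The cost is a short SAP rewording and possibly one data field. The AS-3-only comparison uses fewer REF AUCs and is less precise, so the number of AS-3 REF AUCs should be reported with it.

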## **C. Secondary Efficacy Endpoints Analyses**

Hb increment, proportional decline in post-transfusion Hb and RBC mass infused will each be analyzed separately with a mixed effects repeated measures model fitting fixed effect terms for treatment, period and treatment\*period interaction. Subject will be included in the model as a random effect. The point estimates and associated 95% confidence intervals will be presented for the treatment differences.

Two analyses will be carried out for the 15 minute Hb value.

- The first is directed at estimating the difference between the MIR RBC and REF RBC products and for this the mixed-effect model used for the primary outcome will be adopted to model the 15 minute Hb value as the response. A 95% confidence interval for the estimated mean difference in the 15 minute Hb value will be computed.
- A second analysis will report the proportion of 15 minute Hb values within the pre-specified range of plus or minus 15% of the target value. This target value is specified at the start of study and should remain fixed during the course of the study. This success rate will be estimated using generalized estimating equations with this binary response, a logistic link, a main effect for product type (MIR vs. REF RBCs) and an exchangeable correlation matrix to accommodate the dependence within patients. The resulting estimates will be provided as supplementary information to help in the

interpretation of the primary analyses. There will be no non-inferiority bound or formal tests associated with these event rates.

All secondary endpoints will be descriptively summarized by treatment. Additionally, Hb increment, proportional decline in post-transfusion Hb and RBC mass infused will be presented graphically.

As a secondary analysis, actual Hb AUC will also be analyzed similarly to the primary endpoint described in Section VIII.B. Specifically, the Hb AUC will not be normalized to the 15-minute post-transfusion Hb level in this analysis.

The frequency of off-protocol transfusions will be estimated during the wash-in period and treatment periods for MIR RBCs and REF RBC products. This frequency will be estimated using generalized estimating equations with this binary response (on- versus off-protocol), a logistic link, a main effect for assigned treatment (MIR RBCs vs. REF RBCs), and an exchangeable correlation matrix to accommodate the dependence within patients. The results of this descriptive analysis will give context to the FAS and PPS non-inferiority analyses. The raw patterns and frequencies of off-protocol transfusions will be reported.

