14.3 With Each RBC Transfusion Episode

The following procedures will be completed before, during, and after each study transfusion unless otherwise noted. These procedures will be completed for all transfusions occurring during the 50 -day wash-in period plus the subsequent 2 transfusion episodes (for endpoint assessment) during each of the 2 crossover treatment periods. The date and time of transfusion, number of units, and type of product transfused will be documented in the eCRF. For off-protocol RBCs transfusion, the following characteristics will also be collected: transfused volume, type of RBC unit (per ISBT code), and hematocrit (if known).

Visits on 1 Day Post Transfusion and 7 Days Post Transfusion may be conducted in the clinic or may utilize a remote nursing visit.

At Baseline the Investigator will identify and document the target post-transfusion (15 min) Hb level; with each transfusion episode, the Investigator will perform the following:

1. Calculate the volume of RBCs required to achieve the target Hb (identified at baseline)
 - a. $[(\text{desired hemoglobin}) - (\text{current hemoglobin})] \times (\text{body weight [kg]}) \times (3/\text{Hct of RBC units}) = \text{mL to transfuse}^{39}$

Note: 3 is constant in the formula above
2. If the post-transfusion (15 min) Hb is under 15% of the target Hb, then an additional transfusion should be considered. If the post-transfusion Hb is over 15% of the target Hb, this will be documented^{39,40}

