### **A. Efficacy Outcomes**

#### **Primary Endpoint**

The primary endpoint is normalized Hb AUC as a measure of the percent surviving RBCs. The normalized Hb AUC is calculated using the trapezoidal method on normalized Hb. The normalization is accomplished by dividing all post-transfusion Hb values by the 15-minute post-transfusion Hb level. The ratio is expressed as a percentage. A natural log-transform of the observed normalized Hb AUC will be utilized.

The normalized Hb AUC is expected to be calculated using four timepoints: the 15-minute post transfusion, 24-hour, Day 7, and end of transfusion interval (ie, pre-transfusion measure for the subsequent interval). If either the 24-hour or Day 7 measure is missing, the AUC will still be calculated using the following rule. If both are missing, or if either the 15-minute post transfusion or the end of transfusion interval are missing, then no AUC will be calculated for that interval.

A single value imputation approach will be used to estimate the missing percent decrease at either the 24 hour or Day 7 (but not both). The median of the observed normalized Hb levels (ie, percent decreases) for the treatment received at that particular time point and transfusion interval number will be used so that the AUC is based on 4 values of normalized Hb. This approach takes advantage of all the observed data rather than assuming an entire AUC is missing in the presence of a single missing Hb value.

The approximations are conservative in the sense that they bias towards inferiority in the case of missing Hb values for the normalized Hb AUC calculation.

The Hb will be collected within 1 hour before transfusion, 15 (+ 5) minutes, 24 ( $\pm$  6) hours, and 7 ( $\pm$  1) days after transfusion and at the end of study treatment follow-up. The transformed normalized Hb AUC values from the first 2 transfusion episodes after the 50-day wash-in for each period will be used to obtain a single measure associated with each treatment. If only a single

normalized Hb AUC value is available after the wash-in for an individual period, that single value will be used for analysis.

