### **Secondary Endpoints**

There are 4 secondary endpoints of interest in this study. No adjustments for multiple comparisons/testing will be performed for the other secondary endpoints. Analyses will be based on the observed data using the FAS.

The secondary endpoints are:

- Hb increment
  - Calculation:  $[(\text{post-transfusion Hb} - \text{pre-transfusion Hb})/\text{Hb transfused}]/\text{RBC volume in subject at pre-transfusion}$
  - Hb transfused in the above formula is the sum of Hb content of each unit transfused calculated as  $(\text{Hb/dL} \times \text{volume})/100$
  - Note: RBC volume in subjects at pre-transfusion is based on weight, height, sex, and pre-transfusion Hct. Example formulas are provided below where weight is in pounds and height is in inches.
  - RBC Volume (Male) =  $[(0.006012 \times \text{height}^3)/(14.6 \times \text{weight}) + 604] \times (\text{Hct}/100)$
  - RBC Volume (Female) =  $[(0.005835 \times \text{height}^3)/(15 \times \text{weight}) + 183] \times (\text{Hct}/100)$
- Actual Hb level post-transfusion (15 min)
- Proportional decline in post-transfusion Hb level
  - Calculation:  $[(\text{Hb (t0)} - \text{Hb(t1)})/\text{Hb(t0)}]/\text{time between transfusion (days)}$
- RBC mass infused (volume x Hb/unit)

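### SAP VIII.C leaves the episode set for RBC mass infused open, and read literally it admits wash-in transfusions whose size reflects the previous product

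*SAP*

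**What the plan says.** For three of the four secondary endpoints, SAP VIII.C (Secondary Efficacy Endpoints Analyses) states: "Hb increment, proportional decline in post-transfusion Hb and RBC mass infused will each be analyzed separately with a mixed effects repeated measures model". The model is specified as "fitting fixed effect terms for treatment, period and" the treatment-by-period interaction, with a random subject effect. It has no transfusion-number term and names no episodes. The only statement about data is in SAP VIII.A (Secondary Endpoints): "Analyses will be based on the observed data using the FAS". Protocol 21.7.1.2 says the same and adds no restriction.

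The primary endpoint is treated differently. SAP VIII.A (Primary Endpoint) says: "The transformed normalized Hb AUC values from the first 2 transfusion episodes after the 50-day wash-in for each period will be used". In the sample code of SAP VIII.B, TRANNUM is defined only for those two transfusions.

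Wash-in data will exist. Protocol 14.3, on procedures at each transfusion, says: "These procedures will be completed for all transfusions occurring during the 50 -day wash-in period plus the subsequent 2 transfusion episodes". Volume transfused is recorded every time. The same section sets the volume as (desired Hb minus current Hb) x body weight x 3 / Hct of the units, with the desired Hb fixed at baseline.

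**The concern.** Under the volume rule, red-cell mass at a transfusion replaces what was lost since the previous one. It therefore measures survival of cells already in the patient, not of the cells about to be given. Neither document describes a washout between periods. The first Mirasol transfusion of a period is sized by loss of conventional cells. In the Mirasol-then-reference sequence, the first reference transfusion is sized by loss of Mirasol cells. Later wash-in transfusions are only partly converted to the new product.

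If wash-in episodes enter, this need is booked to the wrong product and the difference is pulled toward zero. The treatment-by-period term does not remove it, because the misattribution lies within each period and stays in the treatment contrast. Protocol 19.3.3 names more frequent transfusions and/or more units per transfusion as a known risk of the product. RBC mass infused is the secondary efficacy endpoint that shows the per-transfusion part of that risk. An episode set left open could also be chosen after the data are seen.

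**Working it through.** The documents give no planned figure for RBC mass infused, so there is none to reproduce. The size was checked with a scenario.

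**Inputs**
- Linear survival 60.49 days (Mirasol) and 81.57 days (untreated): Protocol 5.2, Table 19-3.
- Mean recovery 82.5% and 91.7%: Protocol 19.3.3.
- Half-lives 22.58 and 35.83 days, for an alternative exponential curve: Table 19-3.
- Intervals of 14, 21 and 28 days: inclusion criterion 1 (2-4 weeks).

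**Assumptions (not in the documents):** fixed interval, exact top-up to target, and steady state on reference cells before day 0.

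**Episodes.** Transfusions before day 50 number 4, 3 and 2 at the three intervals. With the two assessed episodes, wash-in makes up 4/6, 3/5 and 2/4 of each period's data.

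**Formula.** Mass at transfusion k = 1 - sum over earlier transfusions of (mass x surviving fraction), in units of the target circulating mass. Surviving fraction at age t is R(1 - t/L), or R x 2^(-t/half-life).

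**Worked case, 21 days, linear**
- Reference survival: at 21 days 0.917(1 - 21/81.57) = 0.681; at 42 days 0.445; at 63 days 0.209. Steady-state mass = 1/(1 + 1.335) = 0.428.
- Mirasol survival: at 21 days 0.825(1 - 21/60.49) = 0.539; at 42 days 0.252. Steady-state mass = 1/(1 + 0.791) = 0.558.
- Second Mirasol transfusion: 1 - 0.428(0.539 + 0.445 + 0.209) = 0.489.

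| Period | Wash-in episodes | Assessed episodes |
|---|---|---|
| Mirasol (either sequence) | 0.428, 0.489, 0.539 | 0.586, 0.548 |
| Reference after Mirasol | 0.557, 0.483, 0.424 | 0.381, 0.452 |
| Reference first | 0.428 throughout | 0.428, 0.428 |

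- All episodes: Mirasol mean 0.518; reference mean (0.459 + 0.428)/2 = 0.444; difference 0.0745, or +17%.
- Post-wash-in only: 0.567 against (0.417 + 0.428)/2 = 0.422; difference 0.145, or +34%.
- Ratio 0.0745/0.1451 = 0.51.
- First episodes: 0.428 - 0.557 = -0.129 in Mirasol-then-reference, and 0.428 - 0.428 = 0 in reference-then-Mirasol.

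**All intervals, linear survival with recovery loss**

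| Interval | All episodes | Post-wash-in only | Ratio of absolute differences |
|---|---|---|---|
| 14 days | 0.062 (+19%) | 0.135 (+46%) | 0.46 |
| 21 days | 0.075 (+17%) | 0.145 (+34%) | 0.51 |
| 28 days | 0.077 (+14%) | 0.154 (+29%) | 0.50 |

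Across linear or exponential survival, with or without the recovery loss, the ratio is 0.39-0.51.

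**The other two endpoints.** The decline over the interval after each transfusion, under the same comparison, has a ratio of 0.72-1.05 (linear) and 0.62-0.77 (exponential). Hb increment divides the Hb rise by the Hb transfused, so a larger need left by the previous product is not credited as such. The previous product enters only through the pre-transfusion RBC-volume divisor. No attenuation figure was derived for it.

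**The case against.** **The SAP does not say that wash-in episodes are included.** This is correct. A reader might infer that the plan has chosen to model all transfusions, but the documents support only that the episode set is unstated. The reference to observed data can be read as ruling out imputation, not as selecting episodes. SAP VIII.C names the wash-in where it wants it: "The frequency of off-protocol transfusions will be estimated during the wash-in period and treatment periods for MIR RBCs and REF RBC products". In the same section, the 15-minute Hb mean comparison borrows the primary model, and actual Hb AUC is analysed like the primary endpoint. All this makes the restricted reading possible. It does not settle the matter, because these three endpoints have their own model, without TRANNUM, and nothing excludes wash-in data.

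**The post-wash-in value is not the truth either.** In the scenario it is 1.12-1.35 times the steady-state difference under linear survival and 0.64-0.73 times under exponential. Part of the halving under linear survival is therefore overshoot in the comparator. Against steady state, however, the all-episode estimate is still only 0.53-0.57 (linear) or 0.26-0.34 (exponential), so the dilution stands.

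**The scenario is idealised.** The survival figures come from autologous cells stored 21 days and reinfused into healthy volunteers. Reference units here may be older, irradiated or washed. Protocol 10.1 leaves both volume and frequency to the physician. If extra need is met by shorter intervals, mass per episode misses it; Protocol 19.3.3 says frequency will be evaluated. These limits apply to the size, not to the mechanism, which follows from the volume rule when intervals are held.

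**The stakes are limited.** These secondary results are estimates with 95% intervals and no non-inferiority bound, and the primary conclusion is untouched. This stands.

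**Conclusion.** The point holds as an unspecified episode set that matters for RBC mass infused. If wash-in transfusions enter, as the text literally allows, the Mirasol-minus-reference difference in mass per episode falls to about 0.4-0.5 of its post-wash-in value, in favour of the test product. First-episode contrasts are reversed in Mirasol-then-reference and zero in reference-then-Mirasol. These sizes are conditional on fixed intervals, exact top-up and healthy-volunteer survival; they are not predictions for this population.

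Two stronger readings fail. One is that all three secondary endpoints are halved: proportional decline ranges from about 0.6 to no attenuation depending on interval and survival curve, and halving is not shown for Hb increment. The other is that first-episode contrasts have the wrong sign in both sequences: in reference-then-Mirasol both first transfusions follow reference cells. The SAP should be corrected before database lock, but the non-inferiority test is not at risk from this point.

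**What to change.** In SAP VIII.C, state that RBC mass infused is modelled on the same two post-wash-in episodes per period as the primary endpoint, with TRANNUM added to the fixed effects. Apply the same rule to Hb increment and proportional decline for consistency. Summarise wash-in episodes separately and descriptively.

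This takes one sentence and a data filter, with no new data collection. The price is that half to two thirds of the episodes leave these models, so the intervals will be somewhat wider. For RBC mass, the episodes dropped are those that wholly or partly carry the previous product's survival.
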